## 9.9.3. Discharge Visit

This visit will be conducted at date of discharge or 7 days post procedure, whichever comes first. The following data are to be collected:

- Cardiac rhythm will be documented, measured as per standard practice (ECG/Holter)
- Heart failure symptoms (such as dyspnea, persistent coughing, edema, fatigue, nausea, orthopnea, confusion, increased heart rate) will be collected and results of physical examination (such as systolic and diastolic blood pressure, NYHA class) will be documented
- Medication – The drug therapy provided to the subject at discharge visit will be documented
- Serious Adverse Events including MACCE (as defined in section 11.1) since the implant will be documented, and an Adverse Event form will also be filled out
- Echocardiography – Transthoracic echo (TTE) data will be collected, documenting mitral valve regurgitation grade, mitral gradient and coaptation, right/left atrial, ventricular size and functional information (including aortic and tricuspid evaluation), etc.

## 9.9.4. 3-6 month Follow Up

This visit will be conducted between 90 days up to 210 days post procedure, whichever comes later. The following data are to be collected:

- Cardiac rhythm will be documented, measured as per standard practice (ECG/Holter)
- Heart failure symptoms (such as dyspnea, persistent coughing, edema, fatigue, nausea, orthopnea, confusion, increased heart rate) will be collected and results of physical examination (such as systolic and diastolic blood pressure, NYHA class) will be documented
- Medication – The drug therapy provided to the subject since last visit will be documented

- Serious Adverse Events including MACCE (as defined in section 11.1) since the implant will be documented, and an Adverse Event form will also be filled out
- Echocardiography – Transthoracic echo (TTE) data will be collected, documenting mitral valve regurgitation grade, mitral gradient and coaptation, right/left atrial, ventricular size and functional information (including aortic and tricuspid evaluation), etc.

## 9.9.5. 12 month Follow Up

This visit will be conducted up to 395 days (365 days +/- 30 days) post procedure. The following data are to be collected:

- Cardiac rhythm will be documented, measured as per standard practice (ECG/Holter)
- Heart failure symptoms (such as dyspnea, persistent coughing, edema, fatigue, nausea, orthopnea, confusion, increased heart rate) will be collected and results of physical examination (such as systolic and diastolic blood pressure, NYHA class) will be documented
- Medication – The drug therapy provided to the subject since last visit will be documented
- Adverse Events since last visit will be documented, and an Adverse Event form will also be filled out
- Echocardiography – Transthoracic echo (TTE) data will be collected, documenting mitral valve regurgitation grade, mitral gradient and coaptation, right/left atrial, ventricular size and functional information (including aortic and tricuspid evaluation), etc.

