**Medtronic Confidential**

This document is electronically controlled

056-F275, v3.0 Clinical Investigation Plan Template

		Aortic and Tricuspid valves HF parameters (LVEF, LVEDD, LAD, etc.)
12 Month Follow Up (data reported up to day 395 (365 +/- 30 days) post procedure date will be collected)	Health Assessment	Subject Assessment (Cardiac rhythm, NYHA, etc.) Serious Adverse Events including major adverse cardiac or cerebrovascular events (MACCE) as defined in section 11.1 Medication
	Echo	MR Mitral Gradient Leaflet coaptation Aortic and Tricuspid valves HF parameters (LVEF, LVEDD, LAD, etc.)
	Study Exit	Exit

The following figure (Figure 3) is indicative of the study methods.

Figure 3: Study Methods

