## 9.8. Assessment of Safety

Serious Adverse Events and Device Deficiencies throughout the study will be collected and recorded in the AE and DD CRF's. All Adverse Events and Device Deficiencies will be reviewed by Medtronic Safety Representative. Safety Representative will ensure the timely review and reporting of all events. Safety assessment will be documented in the safety database. The types of events and reporting requirements are described in section 11 below.

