**Medtronic Confidential**

	Baseline / Pre-Operative (data from most recent assessment from planned implant date preferred, not exceeding 60 days)	Implant	Discharge (date of discharge or 7 days post procedure, whichever comes first)	3-6 month Follow Up (data reported from 90 days up to 210 days post procedure, whichever comes later)	12 month Follow Up (data reported up to day 395 (365 +/- 30 days) post procedure date will be collected)
Mitral Valvular Lesion and Risk Factors	X				
Cardiac Rhythm Assessment	X		X	X	X
Heart Failure Symptoms	X		X	X	X
NYHA Classification	X		X	X	X
Medications	X		X	X	X
Echocardiography including MR grade, mitral gradient, coaptation, LVEF, LVEDD, LAD and tricuspid and aortic valve assessments	X	X 	X	X	X
Implant Details		X			
Concomitant Procedures		X			
Re-operation			X	X	X
Serious Adverse Events including MACCE (as defined in section 11.1)		X	X	X	X
Device Deficiency		X	X	X	X
Death			As they occur		
Protocol Deviation			As they occur		
Study Exit					X

(1) TEE specific parameters will be collected for TEE done at implant

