## 9.9.2. Implant Visit

The implant will be performed as per surgeon's discretion and standard practice. The following information will be collected during the implant procedure.

- Details of surgical approach and procedural complexity (cross-clamp time, concomitant procedures, etc) will be documented
- Mitral valve pathology (valve dilatation, calcification, prolapse, etc) and leaflet segments affected (A1, A2, A3, P1, P2, P3) will be documented
- Details of mitral repair along with the ring/band annuloplasty (papillary muscle repair, chordal replacement or shortening, etc) and sizing of mitral valve annulus will be documented
- Serious Adverse Events including MACCE (as defined in section 11.1) during the implant will be documented, and an Adverse Event form will also be filled out
- Echocardiography – Transoesophageal echo (TEE) data will be collected, documenting various TEE parameters routinely evaluated during annuloplasty procedure.

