**7.9.9 Secondary Endpoint #7**

New onset of atrial fibrillation (AF), as evaluated through follow up ECG at discharge, first follow up (3-6 months) and at second follow up (12 months), as well as on the AE form.

Hypothesis/Decision criteria:

No specific hypotheses or pass/fail criteria have been set. The analysis will be descriptive and no statistical hypothesis test will be performed.

Endpoint Definition/Parameters to Be Estimated:

New onset of AF is defined as when the subject did not present with prior history of AF at baseline nor was AF detected at baseline visit, but AF did manifest post procedure and was either diagnosed during the study visits (discharge, 3-6 months or 12 months visit) or was otherwise diagnosed during the duration of subject participation in the study.

Data Collection and Analysis Dataset:

Data will be collected on a DISCHARGE/FOLLOW UP (SV) CRF or an AE CRF.

This objective will be analyzed for the Successfully Implanted (IMP) cohort.

Analysis Method:

A Kaplan-Meier analysis will be performed.

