## **7.10 Safety Evaluation**

Primary and secondary safety endpoints will be summarized as noted in Section 7.9 of this Statistical Analysis Plan (SAP). Adverse events will be provided in a listing for all attempted implant subjects. The proportion of subjects experiencing events will also be summarized by MEDDRA coding (System Organ Class and High Level Term) for successfully implanted and attempted but not successfully implanted subjects.

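### The CIP contradicts itself on adverse event scope, and non-serious atrial fibrillation between visits has no specified route into the new-onset AF analysis

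*Combined protocol and SAP*

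**What the plan says.** CIP 9.8 sets the general rule: "Serious Adverse Events and Device Deficiencies throughout the study will be collected and recorded". The Schedule of Events in CIP 9.1 repeats the serious-only scope at implant and at every later visit, 12 months included: "Serious Adverse Events including major adverse cardiac or cerebrovascular events (MACCE) as defined in section 11.1". Table 4 marks the same scope at the same four points and has no row for non-serious events. The implant instruction in 9.9.2 reads "Serious Adverse Events including MACCE (as defined in section 11.1) during the implant will be documented". For discharge and 3-6 months, 9.9.3 and 9.9.4 read "Serious Adverse Events including MACCE (as defined in section 11.1) since the implant will be documented".

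The 12 month instruction in 9.9.5 drops the word serious: "Adverse Events since last visit will be documented, and an Adverse Event form will also be filled out". Section 9.11 also describes the 12 month visit as collecting all adverse event information, and refers to the timelines in 11.2. The investigator table in 11.2 covers serious events, device deficiencies and new safety information. The list of non-reportable events in the same section is framed as a set of exemptions, as if adverse events in general were reportable.

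In SAP 7.9.9, new-onset AF includes AF found at a study visit and AF that "was otherwise diagnosed during the duration of subject participation in the study". The named sources are the discharge/follow-up form and the adverse event (AE) form. SAP 7.12 replaces simple percentages with a Kaplan-Meier analysis of AF seen on a post-procedural ECG or on AE forms. SAP 7.10 lists adverse events without a seriousness limit and adds: "The proportion of subjects experiencing events will also be summarized by MEDDRA coding".

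**The concern.** The AF definition is wider than the data collection that feeds it. AF between visits counts towards the endpoint, and the AE form is the only evident way for it to reach the database. Up to the 3-6 month visit that form is requested for serious events only. A non-serious episode that starts and resolves between two visit recordings meets the definition but need not be written down anywhere.

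The 12 month wording adds a second problem: a site cannot tell from the CIP whether a non-serious event belongs on the form at that visit. Sites may then differ, and the registry's AE tables and AF curve would depend on which section each site followed.

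**Working it through.** The plan has no figure to reproduce. SAP section 6 states that the 200 subjects were not statistically derived, and neither document gives an expected AF rate. The check compares the sections and works through the visit windows.

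**Step 1. Scope by section**

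| Place | Applies to | Scope |
|---|---|---|
| CIP 9.8 | whole study | serious events, device deficiencies |
| CIP 9.1 Schedule of Events | implant, discharge, 3-6 and 12 months | serious, including MACCE |
| CIP Table 4 | the same four points | serious, including MACCE |
| CIP 9.9.2 to 9.9.4 | implant, discharge, 3-6 months | serious, including MACCE |
| CIP 9.9.5 | 12 months, back to the last visit | all adverse events |
| CIP 9.11 | 12 months | all adverse events, on the 11.2 timelines |
| CIP 11.2, investigator table | whole study | serious events, device deficiencies, new safety information |
| CIP 11.2, non-reportable list | after the procedure | reads as if all adverse events are reportable unless exempt; transient arrhythmia is exempt only during the procedure (0 hours) |

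**Step 2. How a new AF case can reach the analysis**

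- AF present at a visit: recorded as cardiac rhythm by ECG or Holter (9.9.3 to 9.9.5), whatever its seriousness. Its event time may be the visit date rather than the onset date.
- AF that causes or prolongs a hospital stay: can qualify as serious under 11.1 and so reach the AE form.
- Non-serious AF diagnosed off-visit and absent at the next recording: counted by the definition, with no specified route.

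**Step 3. How long the third type goes uncollected**

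Inputs: discharge data by day 7 at the latest (9.9.3); 3-6 month visit on days 90 to 210 (9.9.4); 12 month visit on day 365 plus or minus 30, so days 335 to 395 (9.9.5).

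- With discharge data on day 7, the off-visit interval before the 3-6 month visit is 90 - 7 = 83 days at the shortest and 210 - 7 = 203 days at the longest. Earlier discharge lengthens both.
- If 9.9.5 and 9.11 govern, serious-only collection ends at the 3-6 month visit: 90/365 = 25% to 210/365 = 58% of the first year. The all-event period that follows lasts from 335 - 210 = 125 days to 395 - 90 = 305 days.
- If 9.8, the Schedule of Events and Table 4 govern, serious-only collection covers the whole follow-up.

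**Step 4. Effect on the analyses**

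SAP 7.2 reads the Kaplan-Meier curves at days 7, 183 and 365. If 9.9.5 and 9.11 govern, each subject moves to wider capture somewhere between day 90 and day 210. Day 183 lies inside that window, so the 6 month AF estimate would combine subjects under both scopes, and the MedDRA proportions in SAP 7.10 would add serious-only time to all-event time. If the tables and 9.8 govern, the scope is uniform, but SAP 7.10 then gives a general adverse event label to serious-only data.

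Under either reading the collection gap only removes qualifying cases, so it can only lower the AF rate.

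**The case against.** The strongest reply is that 9.9.5 is loose wording. The Schedule of Events, Table 4 and 9.8 all say serious only at 12 months, 9.11 ties collection to 11.2, whose investigator table names serious categories, and at every other visit serious events also go on a form called an adverse event form. On that reading there is one scope and nothing is mixed. This stands as far as it goes: a reader might infer that the AE tables certainly mix two scopes, and the documents do not settle that. But the same reading extends the AF gap to the whole follow-up.

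A second reply is that the case report forms are not in the documents, so the discharge/follow-up form might ask about AF since the last visit. That is possible, but no section says so, and SAP 7.12 names only post-procedural ECGs and AE forms. The non-reportable list also suggests that later arrhythmia is reportable. This weakens any claim that non-serious AF is deliberately excluded, but it deepens the inconsistency. Likewise, 9.11 gives no look-back period and might be stretched to recover earlier events at 12 months, but 9.9.5 looks back only to the previous visit.

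Third, this is one descriptive secondary endpoint of eight in a registry with no hypothesis tests. That is correct and limits the severity.

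**Conclusion.** The contradiction is on the page, and the AF gap exists up to the 3-6 month visit whichever section governs the 12 month visit. Followed as written, the plan gives an AF rate biased low. The mixing of scopes, along the AF curve and in the SAP 7.10 proportions, is conditional on sites following 9.9.5 and 9.11.

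The size cannot be derived. A reader might assume a true 12 month AF rate of 20% to 30% with 25% to 50% of cases missed, and infer a loss of 20% x 0.25 = 5 to 30% x 0.50 = 15 percentage points. Neither input has any basis in the documents, and removing that share of all 12 month cases fits only a serious-only scope for the whole year. If 9.9.5 governs, non-serious cases in the last interval are collected and the loss would be smaller. Nor is all non-serious AF lost, since AF present at a visit is recorded.

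The primary endpoints are not affected: deaths are serious events and MR grade comes from echo. Stroke, heart failure hospitalization and re-intervention fall under MACCE or have their own form. The conclusion assumes that the forms follow the CIP and SAP text. The correction should be made, but it is not critical.

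**What to change.** Set one scope and use it in CIP 9.1 (Schedule of Events), 9.8, Table 4, 9.9.2 to 9.9.5, 9.11, and both the investigator table and the non-reportable list in 11.2. A workable scope is serious adverse events including MACCE, plus any new-onset AF regardless of seriousness, entered on the AE form with its onset date. Device deficiencies stay as they are.

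In SAP 7.10, label the listing and MedDRA tables by that scope: tabulate serious events there, and report non-serious AF under the AF endpoint in 7.9.9. Merely restricting 7.10 to serious events, without that pointer, would leave the added AF entries out of the safety section with no explanation.

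The cost is a minor CIP amendment, an eCRF completion guideline and a few more event entries per site. If enrolment is already advanced, some off-visit AF could still be recovered from the hospital records and Holter reports that 9.9.6 lists as source documents.

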## 9.9.6. Source documents

Source data are all information, original records of clinical findings, observations, or other activities in a clinical trial necessary for the reconstruction and evaluation of the trial. Source data are contained in source documents. Examples of these original documents, and data records include but not limited to: hospital records, clinical and office charts, laboratory notes, memoranda, or evaluation checklists, pharmacy dispensing records, recorded data from automated instruments such as hospital monitoring equipment, Holter portable document format (PDF) reports, copies or transcriptions certified after verification as being accurate and complete, microfiches, photographic negatives, microfilm or magnetic media, x-rays, subject files, and records kept at the pharmacy, at the laboratories, and at medicotechnical departments involved in the clinical trial.

The investigator will clearly mark clinical records to indicate that the subject is enrolled in this clinical study.

The site is responsible to record all trial related source data enabling the sponsor to reconstruct the complete course of the clinical trial. Source data will be transcribed to and reported through the CRF accordingly. A source data identification list will be provided to the sponsor for approval prior to commencing the clinical part of the trial. The list will be filed in the investigator site file.

Where copies of the original source document as well as printouts of original electronic source documents are retained, these shall be signed and dated by a member of the investigation site team with a statement that it is a true reproduction of the original source document.

## 9.10. Deviation Handling

A protocol deviation is defined as an event where the clinical investigator or site personnel did not conduct the study in accordance to the protocol or the Investigator agreement. The investigator is not allowed to deviate from these documents except with prior approval and under emergency circumstances. All deviations shall be documented and explained, regardless the reason for the deviation.

Examples of protocol deviations include but are not limited to the following:

- Failure to obtain informed consent prior to participation
- Incorrect version of the informed consent form used
- Failure to obtain EC/IRB approval before the start of the study
- Subject did not meet inclusion/exclusion criteria
- Source data permanently lost
- Enrollment of subjects during lapse of EC/IRB approval

Investigators should obtain prior approval from Medtronic before initiating any change or deviation from the CIP, except where necessary to protect the life or physical wellbeing of a subject in an emergency situation. Such approval shall be documented in writing and maintained in the investigator site files. Prior approval is generally not expected in situations where unforeseen circumstances are beyond the investigator's control (eg. subject did not attend scheduled follow-up visit).

Deviations will be reported to Medtronic regardless of whether medically justifiable, pre-approved by Medtronic, or taken to protect the subject in an emergency. Study deviations should be reported to Medtronic vide the study Deviation eCRF (1 eCRF for each protocol deviation). Relevant information for each deviation will be documented on a deviation form completed by site personnel and reviewed by the Investigator.

Investigators should report the following deviations to Medtronic and their reviewing EC/IRB in accordance with reporting requirements of local EC/IRB:

- Failure to obtain written informed consent
- Deviations to protect the life or physical well-being of a subject in an emergency

In addition, Investigators are required to adhere to local EC/IRB procedures for reporting deviations.

Medtronic is responsible for analyzing deviations, assessing their significance, and identifying any corrective and/or preventive actions that may be warranted such as amending the CIP, in accordance with Medtronic SOPs. Repetitive or serious investigator non-compliance may represent a need to initiate a corrective action plan, which may include suspension of enrollment or termination of the investigator's or site's participation in the study.

### Request for approval of study deviations

The investigator shall obtain documented approval from Medtronic, before implementation, for any change in- or deviation from the CIP. In case of any deviations that can affect the subject's rights, safety and well-being or the scientific integrity of the clinical study, approval from the EC/IRB and regulatory authority must also be obtained before implementation. The investigator shall timely contact the Clinical Manager for review of the proposed change/deviation.

Prior approval is not always realistic in situations where unforeseen circumstances are beyond the investigator's control. However, also in these cases, the event is considered a deviation, and shall be reported.

In any emergency situation the investigator shall exercise his/her judgment to safeguard the subject's interest. Such deviations from the CIP do not require the prior approval of Medtronic. The investigator shall report the deviation as soon as possible to Medtronic and the reviewing EC/IRB, if applicable.

## 9.11. Subject Withdrawal or Discontinuation

All subjects will be encouraged to remain in the registry through the last follow-up visit at 12 months. Subjects who discontinue participation prematurely after attempted implant will be included in the analysis of results (as appropriate) but they will not be replaced in the enrollment of total study subjects. If a study subject is discontinued from the study early, the reason for discontinuation should be documented in the subject file and a Study Exit eCRF must be completed. If discontinuation is because of safety concerns, the subject shall be asked to be followed for collection of ongoing safety data outside the study. Any data collected after the exit date will not be analyzed as part of the study.

In case the subject undergoes device explant, the subject will be exited from the study.

The subjects will be exited from the study following their 12 month follow up visit. This 12 month visit will be primarily conducted via in-office visit and has a window period of additional 1 month, up to day 395 post implant. All adverse event information will be collected and reported during this follow up visit, as per timelines described above in section 11.2; subjects will be considered exited from the study on completion of their 12 month visit or when they are considered lost to follow up (after three failed attempts are made to contact the subjects).

The investigating site and Sponsor will make every effort to have all subjects complete the follow up visit schedule. A subject will not be considered lost-to-follow-up unless all efforts to obtain compliance are unsuccessful. At a minimum, the effort to obtain follow-up information must include three attempts to make contact via telephone and if contact via phone is not successful, a traceable letter from the Investigator must be sent to the subject's last known address. Should both telephone and mail efforts to contact the subject be unsuccessful, the subject's primary physician should be contacted. Subjects will then be deemed lost to follow up. All contact efforts to obtain follow-up must be documented in the subject's medical records.

If a subject discontinues the study at any time, is withdrawn from the study early, or completes all protocol required follow-up they should then be followed per the local standard of care for their condition.

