## 5.2. Endpoints

### 5.2.1. Primary Endpoint

To evaluate clinical outcomes at 12 months post procedure:

1. Improvement in MR (grade)

This will be determined by assessing the level of mitral valve regurgitation using echo, in subjects at 12 months post procedure compared to the level at baseline. The levels of regurgitation, level 0-4, will correspond to the ASE guidelines ranging from no MR, Mild MR, Moderate MR, Moderate-to-Severe MR and Severe MR, as described in Table 1 above.

2. All cause mortality

All deaths occurring from any cause post procedure.

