### 7.2 General Methodology

Descriptive statistics will be used to report study data. For continuous variables (e.g. age), the mean, median, standard deviation, minimum, maximum, and first and third quartiles will be presented. For categorical variables, the number and percentage of subjects in the category of interest will be presented. For time to event data, Kaplan-Meier analyses of event or event-free rates at discharge, 6 and 12 months will be presented. For these analyses, the time points will correspond to 7 days, 183 days and 365 days post implantation respectively. At each time point with data, the product limit estimate of the event or event-free rates, and the loglog transformed 95% confidence interval using the Peto standard error will be presented. For subjects without an event, the date of censoring will be the latest date of all follow-up visits (including phone and/or mail correspondence), assessments, events (including death) and study exits. For subjects whose exit reason is lost to follow-up, the last follow-up date will be the latest date of the follow-up visits (including phone and/or mail correspondence), assessments and events.

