**Endpoint Definition/Parameters to Be Estimated:**

All-cause mortality event rate estimate will be provided at 12 months post procedure.

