**7.9.6 Secondary Endpoint #4**

Hospitalization for Heart Failure at 6 and 12 months post procedure.

Hypothesis/Decision criteria:

No specific hypotheses or pass/fail criteria have been set. The analysis will be descriptive and no statistical hypothesis test will be performed.

Endpoint Definition/Parameters to Be Estimated:

Hospitalization for Heart Failure event rate estimate will be provided at 6 and 12 months post procedure.

Data Collection and Analysis Dataset:

Data will be collected on an AE CRF.

This objective will be analyzed for the Successfully Implanted (IMP) cohort.

Analysis Method:

A Kaplan-Meier analysis will be performed.

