**7.9.8 Secondary Endpoint #6**

Stroke at 6 and 12 months post procedure.

Hypothesis/Decision criteria:

No specific hypotheses or pass/fail criteria have been set. The analysis will be descriptive and no statistical hypothesis test will be performed.

Endpoint Definition/Parameters to Be Estimated:

Stroke event rate estimate will be provided at 6 and 12 months post procedure.

Data Collection and Analysis Dataset:

Data will be collected on an AE CRF.

This objective will be analyzed for the Successfully Implanted (IMP) cohort.

Analysis Method:

A Kaplan-Meier analysis will be performed.

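### Explanted subjects leave the registry and their later data are dropped, although the mortality endpoint is all deaths to 12 months

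*Combined protocol and SAP*

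**What the plan says.** CIP 9.11 states "In case the subject undergoes device explant, the subject will be exited from the study", and also "Any data collected after the exit date will not be analyzed as part of the study". For an early discontinuation it asks that the reason be documented and that "a Study Exit eCRF must be completed". It does not say whether exit after explant falls on the day of explant, at discharge from that admission, or when the form is completed.

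The endpoints run to fixed times after the procedure:

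- **Primary endpoint 2, mortality.** CIP 5.2.1: "All deaths occurring from any cause post procedure". SAP 7.9.2: "All-cause mortality event rate estimate will be provided at 12 months post procedure".
- **Secondary endpoint 4.** SAP 7.9.6: "Hospitalization for Heart Failure event rate estimate will be provided at 6 and 12 months post procedure".
- **Secondary endpoint 6.** SAP 7.9.8: "Stroke event rate estimate will be provided at 6 and 12 months post procedure".

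All three are analysed by Kaplan-Meier. On censoring, SAP 7.2 says "For subjects without an event, the date of censoring will be the latest date of all follow-up visits", and the same sentence adds contacts, assessments, events and study exits to the candidate dates. A separate date rule exists for subjects lost to follow-up, but none for explant.

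**The concern.** The endpoint definitions place no limit to time with the device in place, yet the exit rule ends observation when the device comes out. A death after explant and exit meets the definition of a primary endpoint and cannot be analysed. Strokes and heart failure hospitalizations are treated the same way.

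Kaplan-Meier is unbiased only if censored subjects share the later risk of those still followed. CIP 10.1 lists explant among the consequences of device complications, in the same list as permanent disability and death. Censoring at explant is therefore likely to be informative. If risk after explant is higher than in other subjects, the reported rates are too low; if it is lower, they are slightly too high.

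The missing link between exit date and explant date adds a second problem. Two programmers could classify a death a few days after the explant operation differently, and both would be following the plan.

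**Working it through.** **Does any other section resolve the conflict?**

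- CIP Table 4 collects deaths throughout, but CIP 9.11 removes those after exit.
- CIP 9.11 provides for continued safety follow-up when a subject stops for safety reasons, but places it outside the study, so it is not analysed.
- SAP 7.1.1 counts explanted subjects but not their later survival.
- SAP 7.4 does not allow a partial event date to be resolved to after study exit.
- SAP 7.9.2 plans Kaplan-Meier only, with no competing-event or sensitivity analysis.
- SAP 7.12 lists changes from the CIP and does not mention explant.

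None of these resolves it.

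**Size for mortality.** The plan has no figure to reproduce: N = 200 is stated not to be statistically derived, and no mortality or explant rate is given. Everything below except N is an assumption.

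Let e be the share explanted, m the mortality by 12 months after explant, and 5% the mortality in other subjects. Then true mortality = 0.05(1 − e) + e·m. The curve censored at explant reports about 5.0%.

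| e | m = 0% | m = 5% | m = 10% | m = 30% |
|---|---|---|---|---|
| 2% (4 subjects) | 4.90% | 5.00% | 5.10% | 5.50% |
| 3% (6 subjects) | 4.85% | 5.00% | 5.15% | 5.75% |
| 5% (10 subjects) | 4.75% | 5.00% | 5.25% | 6.25% |

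Deaths not counted = 200·e·m, from 0 to 200 × 0.05 × 0.30 = 3. The direction reverses at m = 5%.

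A simulation of 4 million subjects (constant hazard giving 5% at 12 months, e = 2% or 5%, explant spread over 12 months or within 90 days) gave 4.98–5.02% for the censored curve. True mortality was 4.76–4.96% at m = 0, 5.11–5.36% at m = 10% and 5.50–6.34% at m = 30%. The small differences from the table reflect explant timing, which the formula ignores.

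**Direct product-limit check.** N = 200, explants at day 60, later deaths at day 75:

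| Other deaths | Explants | Deaths after explant | Censored at exit | Followed |
|---|---|---|---|---|
| 6 | 6 | 2 | 3.06% | 4.00% |
| 6 | 10 | 5 | 3.11% | 5.50% |
| 12 | 6 | 2 | 6.14% | 7.00% |
| 12 | 10 | 0 | 6.24% | 6.00% |
| 12 | 10 | 5 | 6.24% | 8.50% |

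Over the full grid (2, 6 or 10 explants, 0–50% of them dying), followed minus censored runs from −0.24 to +2.39 points. Each missed death is worth about 1/200 = 0.5 point.

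**Effect of the undefined exit date.** Take 6 other deaths, 6 explants at day 60, and 1, 2 or 3 deaths five days after explant. If exit is the day of explant, the estimate is 3.06% in every case. If exit is ten days later, it is 3.55%, 4.04% or 4.53%.

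**Sampling error for scale.** The exact 95% interval for 10/200 is 2.42–9.00%. For the SAP's log-log interval with the Peto standard error at S = 0.95:

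- 190 at risk: SE = 0.95 × √(0.05/190) = 0.0154, giving 2.72–9.09% for mortality.
- 95 at risk: SE = 0.95 × √(0.05/95) = 0.0218, giving 2.11–11.60%. This assumes that half the subjects have their final visit between day 335, when the window opens, and day 365.

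**The case against.** The strongest reply is that this is a boundary, openly stated. CIP 5.2.1 says what counts as a death, CIP 9.11 says how long a subject is observed, and a registry of a device may reasonably stop at explant. Every exit has a recorded date, and only data after it are excluded, so a death on the day of explant is not lost if exit is dated that day or later. Explants are visible in the disposition summary and largely so through the re-intervention curve (SAP 7.9.7). The study is descriptive, with no pass/fail criterion, and CIP 10.1 calls the complications infrequent.

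Much of this stands. The exit is dated; what is missing is its relation to the explant, so the ambiguity mainly concerns later days of the same admission. The bias is probably small, and its size rests wholly on assumed rates. Stopping at explant would be coherent if the endpoint said so, but it says all deaths, estimated to 12 months. Counting explants does not show what happened to those subjects afterwards. In a descriptive registry the estimate is the product, so it should match its definition.

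**Conclusion.** The concern holds. Applied literally, the plan omits qualifying deaths, strokes and heart failure hospitalizations after explant and exit. The result is a 12-month rate that treats explanted subjects as having the same later risk as everyone else.

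For mortality, under 2–5% explanted, 5% mortality otherwise and 0–30% after explant, the truth lies between 0.25 points below and 1.25 points above the reported 5.0%. The more extreme 2.39-point gap needs 10 explants and half of those subjects dying. No size can be given for stroke or heart failure hospitalization. The likely shift is small next to sampling error and does not stop the registry from reporting mortality. It should still be fixed: it affects one primary and two secondary endpoints, the confidence interval does not show it, and few subjects are involved.

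**What to change.** Reconcile CIP 9.11 with CIP 5.2.1.

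**Preferred.** Amend CIP 9.11 so that subjects whose device is explanted stay in the registry to the 12-month visit for vital status, stroke, heart failure hospitalization and serious adverse events. Add to SAP 7.2 that mortality, stroke and heart failure hospitalization are not censored at device explant.

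**If the CIP can no longer be amended**, change the SAP to:

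1. Define the exit date for explanted subjects, and say whether events during the explant procedure or the same admission count.
2. State beside the three curves that they exclude events after explant and exit.
3. Show Kaplan-Meier freedom from death or explant, and the number explanted, beside the mortality curve.

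The composite in step 3 is 1 − 0.95(1 − e), or 6.90%, 7.85% and 9.75% for e = 2%, 3% and 5%. It and the planned curve do not always bracket true mortality. With no deaths after explant, the truth (4.75–4.90%) lies below both.

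**Cost.** The preferred route needs a short amendment with ethics committee approval (CIP 15.6), a few SAP sentences and continued data collection on 4–10 subjects under the assumed rates, some perhaps by telephone. The fallback uses explant and exit dates already collected and needs no new follow-up.
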